4. ANALYSIS SETS

5. STATISTICAL ANALYSES

5.1. General Considerations

The final planned primary analyses will be performed after the completion of the following sequential steps:

- 1. All participants have completed (or withdrawn from) the study as defined in the protocol.
- 2. All required database cleaning activities have been completed and final database release and database lock has been declared by Data Management.

5.1.1. General Methodology

Unless otherwise stated, all hypotheses will be tested at a 2-sided significance level of 0.05 and 95% confidence interval. All continuous measurements will be summarised descriptively at each visit by treatment using observed data.

Summary of continuous variables will be presented using N, Mean, 95% confidence interval of mean, Standard Error of mean (SE), Standard Deviation (SD), Median and Range (Minimum and Maximum). The categorical variables will be presented using number and percentage based on N.

For measurements over time mean values will be plotted to explore the trajectory over time. Observed data will be used as the basis for plotting data along with bars as +/- SE, not otherwise specified.

As a primary analysis, a standard Analysis of Covariance (ANCOVA) will be applied for primary and secondary endpoint to test the significance of the effects of the treatment at Week 26. The model includes treatment as fixed factor and the corresponding baseline value as a covariate.

A parametric Repeated Measures Analysis (RMA) Model will be applied as a secondary analysis to test the significance of the effects of the treatment at Week 2, Week 6, Week 10, Week 14, Week 20 and Week 26 including baseline as covariate.

Presentation of results from a statistical analysis model will include the estimated mean treatment effects (Least Square Means (LSMeans)). For all endpoints analysed statistically, estimated mean treatment differences will be presented together with two-sided 95% confidence intervals and p-values,

HB-adMSCs - Placebo

Pairwise t-test will be performed on the efficacy endpoints to test the difference between baseline and week 26 (EOS) as secondary analysis. Data for all the efficacy outcomes will be checked for normality (Shapiro-Wilk Test).

When there is a larger deviation of data distribution from normality, appropriate nonparametric test will be used.

Study population analyses including analyses of subject disposition, demographic and baseline characteristics, medical history, prior and concomitant medications.

Disposition summary includes, subject screened, randomized and disposition at end of study – Week 26 along with reasons for withdrawals. Subjects in different analysis populations also will be presented.

The screen failure table includes total number of screened subjects and reasons. The percentage in the screen failure table will be calculated based on total number of screened subjects as denominator.

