A total of 80 eligible subjects will be randomized to either placebo or treatment group (HBadMSCs-allogeneic) at screening. The randomization will apply only to eligible subjects. If a subject is not eligible during the screening process for study participation, this subject shall not be randomized to any group.

Randomization will be conducted using the REDCap randomization module. REDCap does not use an algorithm to dynamically randomize subjects but rather a pre-determined, stratified, and permuted randomization schedule. The module allows for creating a custom allocation list, which serves as a lookup table for deciding how to randomize subjects. The allocation table is stratified to achieve balanced distribution within the following subgroups.

- Age: < 43 **(1)** vs. \geq 43 **(2)**
- Average VAS score of Neurological Symptoms:
< 5cm **(1)** and \geq 5 cm **(2)**
- Pre-existing condition prior to COVID-19: Yes **(1)** or No **(2)**

Controlling Blinded Information

REDCap system's user privileges can be used to allow only certain users to set up the randomization, perform the randomization, or view the allocation information. All REDCap end users will be blinded and not access the randomization information, except for the unblinded pharmacist and the randomizer. The randomizer will be responsible for setting up the randomization schedule and performing the randomization.

Blinding for Dose Administration

All subjects, investigators, and the site staff will be blinded to the treatment assigned.

Amber plastic bags shall be used to cover sodium chloride (saline) bags with the product under investigation for infusion. Only subject identification number and date of birth will be on the bag label to ensure proper distribution.

To prepare the investigational product, Unblinded pharmacist (UP) will inject the investigational product into a 250 ml sodium chloride (Saline) infusion bag. This bag should be covered with an amber plastic bag and applied to the label before delivering it to the study site.

Unblinded pharmacists, also identified as Mixer, will keep records of the treatment assigned to each subject in the unblinded pharmacy binder. Access to this pharmacist binder will be limited to the unblinded pharmacist.

Blinding for Clinical Evaluators

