3. STATISTICAL HYPOTHESES

The primary analysis will test whether HB-adMSCs is superior to Placebo according to the following statistical hypotheses:

Null hypothesis H0: The difference in change from baseline to Weeks 26 in Visual Analog Scale of Neurological Symptoms score between treatment groups (HB-adMSCs – Placebo) is equal to zero.

Alternative hypothesis H1: The difference in change from baseline to Weeks 26 in Visual Analog Scale of Neurological Symptoms score between treatment groups (HB-adMSCs – Placebo) is not equal to zero.

Secondary analysis will be tested for mean difference for change from Baseline to Week 26 for efficacy endpoints for both treatment groups,

Null hypothesis H0: $\Delta = 0$ Alternative hypothesis H1: $\Delta \neq 0$

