5.2.2. Main analytical approach

Endpoint/Variables

• Change from baseline in Visual Analog Scale of Neurological Symptoms score following treatment with HB-adMSCs or Placebo at Week 26.

Primary analysis

ANCOVA Model Specification

- To compare the HB-adMSCs to Placebo on Change from baseline to Week 26, a standard Analysis of Covariance (ANCOVA) model will be fitted
- Terms fitted in the mixed effect model will include:

- Primary endpoint efficacy measurements available at Week 26 will be response variable in a linear mixed model using a variance-covariance residual matrix.
- The model will include:
 - Fixed factors: treatment
 - Covariate: baseline
 - Stratification: pre-existing condition prior to COVID-19 (Y/N), average VAS score of Neurological Symptoms (<5cm/>=5cm) and age group (<43/>=43)

Model Checking and Diagnostics

For the ANCOVA Model assumptions will be checked, and appropriate adjustments may be applied based on the data.

Distribution assumptions underlying the model used for analysis will be examined by obtaining a normal probability plot of the residual and a plot of the residuals versus the fitted values (i.e., checking the normality assumption and constant variance assumption of the model respectively) to gain confidence that the model assumptions are reasonable.

Non-parametric analyses, Mann-Whitney U (or Wilcoxon Rank-Sum) Test will be conducted if the normality assumptions does not hold.

Results presentation

Presentation of results from a statistical analysis model will include the estimated mean treatment effects (Least Square Means (LSMeans)) and estimated mean treatment differences will be presented together with two-sided 95% confidence intervals standard error for mean difference and p-value.

Endpoint/Variables

Change from baseline in Visual Analog Scale of Neurological Symptoms score following treatment with HB-adMSCs or Placebo at Week 2, Week 6, Week 10, Week 14, Week 20 and Week 26.

Secondary analysis

Repeated Measures Model Specification

- To compare the HB-adMSCs to Placebo on Change from baseline, a Repeated measures analysis (RMA) model will be fitted
- Terms fitted in the mixed effect model will include:
 - All primary endpoint efficacy measurements available at post-baseline at scheduled measurements will be response variable in a linear mixed model using an unstructured residual covariance matrix.
- The model will include:
 - Fixed factors: treatment and visit
 - Covariate: baseline

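### The SAP lists the primary Week 26 ANCOVA without the randomisation strata in 5.1.1 and with them in 5.2.2, and no rule says which list governs

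*SAP*

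**What the plan says.** SAP section 3 sets one primary null hypothesis, on "The difference in change from baseline to Weeks 26 in Visual Analog Scale of Neurological Symptoms score between treatment groups". SAP 5.1.1 sets the level ("all hypotheses will be tested at a 2-sided significance level of 0.05 and 95% confidence interval") and names the test: "As a primary analysis, a standard Analysis of Covariance (ANCOVA) will be applied for primary and secondary endpoint", at Week 26. Its list of model terms is short: "The model includes treatment as fixed factor and the corresponding baseline value as a covariate".

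SAP 5.2.2, under its primary analysis heading, names the same test: "To compare the HB-adMSCs to Placebo on Change from baseline to Week 26, a standard Analysis of Covariance (ANCOVA) model will be fitted". Its list has treatment and baseline, then a further line that begins "Stratification: pre-existing condition prior to COVID-19 (Y/N), average VAS score of Neurological Symptoms" and goes on to age group, cut at 43 years.

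The Protocol, under Investigational Product Assignment (Randomization and Blinding), uses these same three factors with the same cut-points: "The allocation table is stratified to achieve balanced distribution within the following subgroups".

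**The concern.** The two sections give the analysis the same name, the same role and the same time point, but different terms. Both lists are worded as what the model contains, and neither model is labelled a sensitivity analysis. The exception clause that opens 5.1.1 is attached to the significance level, not to the model terms.

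Two things are at stake. First, stratified allocation balances the arms on the three factors, but an analysis that leaves them out keeps their variation in the residual. If the factors predict outcome, the reported standard error is too large, so the test is conservative and loses power. Second, two candidate models for one primary test leave room to choose after the results are seen.

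**Working it through.** **No plan figure to reproduce.** SAP section 6 and the Protocol's Statistical Methods give 80 subjects without effect size, SD, power or dropout.

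**Inputs from the documents.** Two-sided 0.05 (SAP 5.1.1); 80 subjects (SAP 6); 1:1 allocation (SAP 2.2); three binary strata in a permuted schedule (Protocol). The primary test uses the efficacy analysis set, those who received all four infusions, so 80 is the maximum analysed.

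**Assumed inputs.** Baseline and outcome SD 2 cm apart from strata effects; baseline slope 0.5, so residual SD = 2 × √(1 − 0.25) = 1.73 cm (variance 3.0); blocks of 4; strata of about equal size; age and pre-existing condition each shift the Week 26 score by g = 0, 1 or 2 cm. The VAS stratum is given no effect beyond baseline. If the endpoint is the average score, that stratum is a dichotomised form of nearly the same variable, so the other two factors drive the difference.

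**Approximation for g = 1 cm, effect 1.1 cm.**

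- With strata: SE = 1.73 × 2/√80 = 0.387. Power ≈ Φ(1.1/0.387 − 1.99) = Φ(0.85) ≈ 80%.
- Without strata: each balanced binary factor adds g²/4 = 0.25 to the residual variance, giving 3.0 + 0.5 = 3.5. Reported SE = √3.5 × 2/√80 = 0.418. Because allocation is balanced on the factors, the true sampling SE stays near 0.387.
- The model without strata therefore rejects only if the estimate exceeds 1.99 × 0.418 = 0.832 cm in size. Type I error ≈ 2 × [1 − Φ(0.832/0.387)] = 2 × [1 − Φ(2.15)] ≈ 3.2%. Power ≈ Φ((1.1 − 0.832)/0.387) = Φ(0.69) ≈ 75.5%.

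The approximation takes the balance as perfect. Simulation with incomplete blocks gives slightly higher values: type I error about 4%, power about 76% without strata and 81% with them, and disagreement on significance in about 6% of trials. With g = 0, power is about 81% for both models. Under the null, taking the smaller of the two p-values rejects in about 5.3 to 5.8% of trials.

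**Range over other inputs** (4000 simulated trials per row, stratified blocks of 4):

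| Effect (cm) | g (cm) | Rejects, no strata | Rejects, with strata | Models disagree |
|---|---|---|---|---|
| 0 | 0 | 5.2% | 5.1% | 0.6% |
| 0 | 1 | 3.7% | 5.3% | 2.2% |
| 0 | 2 | 1.4% | 5.4% | 4.0% |
| 0.8 | 0 | 55.0% | 54.5% | 3.8% |
| 0.8 | 1 | 45.6% | 51.4% | 7.4% |
| 0.8 | 2 | 31.9% | 53.1% | 21.5% |
| 1.2 | 0 | 86.3% | 85.7% | 1.9% |
| 1.2 | 1 | 83.1% | 86.6% | 4.0% |
| 1.2 | 2 | 69.3% | 85.7% | 16.5% |

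Section 5.2.2 does not say whether the strata enter as three main effects or as eight cells. In these runs it hardly matters: at 0.8 cm and g = 1, power is 51.4% with main effects and 51.3% with cells.

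**The case against.** The best defence is that 5.1.1 is a general summary and 5.2.2 is the operative specification. Section 5.2.2 sits under the primary endpoint heading and itemises its terms, and 5.3.1 sends the secondary endpoints there for their models. Section 5.1.1 also abbreviates the repeated measures model, leaving out its interactions, strata and covariance structure, and nobody would read that as a rival model. Nor does it say that treatment and baseline are the only ANCOVA terms.

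Much of this stands, and a programmer would probably build 5.2.2. But that is inference, because the SAP states no precedence. Section 5.1.1 cannot be assumed to be a faithful summary either: it makes ANCOVA primary for the secondary endpoints, while 5.3.1 makes the repeated measures model primary for them. SAP 5.4, which reports no departure from the protocol, does not settle it, because the Protocol's Statistical Methods name only a repeated measures mixed model and mention no strata.

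A reader might infer that the primary p-value is wholly open, or that choosing between the models after unblinding would materially inflate the false-positive rate. The documents support neither. The detailed section gives a usable model. Larger figures, about 11.5% disagreement and 7.2% error from picking the better model, arise only if allocation is simulated without stratification, and the Protocol specifies stratified allocation. When the strata are prognostic under that design, the model without them is conservative and adds little to the chance of a false positive.

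**Conclusion.** The inconsistency is real and should be corrected, but its likely consequence is moderate. If 5.1.1 were programmed and age and pre-existing condition each shifted the outcome by 1 cm, the trial would give up about 5 points of power (76% against 81%) and test at about 4% instead of 5%. If the factors are not prognostic, nothing is lost; if they are strongly prognostic, the loss is larger, as the 2 cm rows show. All sizes rest on the assumed SD, baseline slope, effect, strata effects and block size, and on all 80 being analysed. The case rests on lost precision and on a result that can depend on which section is followed, not on inflated type I error.

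**What to change.** Before unblinding, replace the sentence on model terms in 5.1.1 so that it reads: treatment, baseline value and the three randomisation stratification factors as main effects, as specified in 5.2.2. Add the words *as main effects* to the stratification line in 5.2.2 so that the two match, and label any model without strata as a sensitivity analysis.

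The cost is one SAP sentence and three degrees of freedom (residual 77 falls to 74 with 80 analysed).

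This does not settle two separate matters: whether the primary test concerns individual symptom scores or one score, and the switch in 5.2.2 to a Mann-Whitney test when normality is judged not to hold.

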The Sponsor may temporarily or permanently discontinue the clinical trial at any time for safety, ethics, compliance, or other reasons. The study's principal investigator and regulatory authorities will be notified about this decision and the reason for it.

Selection of Clinical Trial Population

Clinical Trial Population

This clinical trial is designed to include adult male and female outpatients with Chronic PostCOVID-19 Syndrome. Study participants who fulfill all the inclusion and none of the exclusion criteria are eligible for participation in the clinical trial. See below eligibility criteria:

Eligibility Criteria

Inclusion Criteria

A study participant will be eligible for inclusion in this study only if all the following criteria apply:

1. Male and female participants 18 – 70 years of age.
2. Participants in the study have proof of Post COVID-19 Syndrome in their medical records.
3. Study participants must have been diagnosed with Chronic post-COVID-19 syndrome for at least four weeks before enrollment in the clinical trial.
4. The study participant is experiencing one or more neurological symptoms for at least 12 weeks, either continually or intermittently, with relapses not experienced pre-illness that interferes with regular daily activities. Symptoms must be new symptoms or dramatic worsening of preexisting symptoms, i.e., the subject didn't have symptoms and had not sought medical treatment for the symptoms before COVID-19, or the symptoms are

dramatically worse (in severity and frequency). At least one symptom must have a severity of “5cm” on the neurological symptom VAS at screening. See the list of symptoms below:

Neurologic Symptoms	- Extreme fatigue	Feeling overtired with low energy and a strong desire to sleep.
	- Brain fog	A diminished mental capacity marked by the inability to concentrate, think, or reason clearly interferes with daily activities.
	- Headache	Sharp or dull reoccurring or intermittent that were not present pre-illness
	- Sleep issues	Any sleep disturbances in sleep quality that makes sleep seem inadequate or unrefreshing like insomnia or hypersomnia.
	- Loss of Taste/Smell	A diminished sense of taste or smell.

5. Study participants should be able to read, understand, and provide written consent.
6. Female study participants should not be pregnant or plan to become pregnant during study participation and six months after the last investigational product administration.

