A repeated measure mixed model will be used to assess within-subject changes from baseline. Correction for multiple comparisons will be employed for post-hoc comparisons. Chronic Post COVID-19 Syndrome's assessments (VAS, FAS, PHQ-9, and SF-36) at infusion 1 (before treatment) will be utilized as a baseline.

Data Handling

Case Report Forms (CRF)

As used in this protocol, the term CRF should be understood to refer to either a paper form or an electronic data record, or both. Reports received by the site, or the central laboratory should be printed, retained as source documentation, and signed by the principal investigator, indicating which values are considered clinically significant and reported as AEs if applicable.

The completion, review, and approval of all CRFs and the completeness and authenticity of all clinical and laboratory data entered on these CRFs are always the Principal Investigator's responsibility. The signature of the Principal Investigator will be required to attest that the information contained on the CRFs is accurate.

Changes in the Conduct of the Clinical Trial

Protocol Amendments

Any change to the protocol will need to have a protocol amendment submitted to the IND, and FDA and IRB must agree before proceeding.

Premature Clinical Trial Termination

Both the Study Investigator and Sponsor have the right to terminate the clinical trial at any time. Should this become necessary, the procedures will be agreed upon after consultation between the two parties. In terminating the clinical trial, the Sponsor and the Study Investigator will ensure that adequate consideration is given to protect the best interests of the study participants. Regulatory authorities and IRB will be informed.

In addition, the Sponsor reserves the right to terminate the participation of any clinical trial site. Conditions that may warrant termination include, but are not limited to:

- Insufficient adherence to protocol requirements
- Failure to enter patients at an acceptable rate
-

Reporting and Publication

Neither the complete nor any part of the study results carried out under this protocol nor any of the information provided by the sponsor to perform the study will be published or passed on to any third party without the consent of the study sponsor.

Any investigator involved with this study is obligated to provide the sponsor with complete test results and all data derived from the study.

Archiving

Investigator File

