 - Stratification: pre-existing condition to COVID-19 (Y/N), average VAS score of Neurological Symptoms (<5cm/>=5cm), and age group (<43/>=43)
- Furthermore, the model will include:

- Interaction terms between treatment and visit
- And Interaction terms between baseline and visit
- Subject will be included as a random factor

Model Checking and Diagnostics

For the Repeated Measures Analysis (RMA) Model assumptions will be checked, and appropriate adjustments may be applied based on the data.

Distribution assumptions underlying the model used for analysis will be examined by obtaining a normal probability plot of the residual and a plot of the residuals versus the fitted values (i.e., checking the normality assumption and constant variance assumption of the model respectively) to gain confidence that the model assumptions are reasonable.

Non-parametric analyses, Mann-Whitney U (or Wilcoxon Rank-Sum) Test will be conducted if the normality assumptions does not hold.

Results presentation

Presentation of results from a statistical analysis model will include the estimated mean treatment effects (Least Square Means (LSMeans)) and estimated mean treatment differences will be presented together with two-sided 95% confidence intervals standard error for mean difference and p-value.

Additional analysis

Summary analysis method

To compare difference between baseline to Week 2, Week 6, Week 10, Week 14, Week 20 and Week 26, a paired t-test will be used for primary endpoint change from baseline VAS to check the statistical significance. Clinical significance will be determined using the established (published) MCID value for the VAS change from baseline. The available MCID value for Change from baseline VAS measure is provided in the Table 1 which will be used as a threshold to evaluate/identify clinically relevant changes.

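### Paired baseline tests and a mean-change MCID rule sit beside the between-arm analyses without a placebo contrast or a descriptive label

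*SAP*

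**What the plan says.** **The between-arm framework.** SAP 3 opens with "The primary analysis will test whether HB-adMSCs is superior to Placebo according to the following statistical hypotheses" and writes the primary null as HB-adMSCs minus placebo. SAP 5.2.2 gives the primary model: "To compare the HB-adMSCs to Placebo on Change from baseline to Week 26, a standard Analysis of Covariance (ANCOVA) model will be fitted". The repeated measures model in the same section has a treatment-by-visit interaction. For the secondary endpoints, SAP 5.1.1 puts ANCOVA first and SAP 5.3.1 puts the repeated measures model first; both compare the arms. SAP 5.1.1 also asks for treatment differences with 95% CIs and p-values for every endpoint that is analysed statistically.

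**The within-arm additions.**
- SAP 5.1.1: "Pairwise t-test will be performed on the efficacy endpoints to test the difference between baseline and week 26 (EOS) as secondary analysis".
- SAP 5.2.2, under additional analysis, names six post-baseline visits and says "a paired t-test will be used for primary endpoint change from baseline VAS to check the statistical significance". Wilcoxon signed-rank is the fallback, and paired p-values are to be shown at all post-baseline visits.
- SAP 5.3.1 repeats the paired tests for the secondary efficacy endpoints.
- SAP 5.2.2 calls an improvement clinically important when mean change from baseline reaches a published MCID (-1.9 in its Table 1). The placebo arm plays no part in that rule.

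**Loose wording elsewhere.** The secondary hypothesis in SAP 3 reads "Secondary analysis will be tested for mean difference for change from Baseline to Week 26 for efficacy endpoints for both treatment groups", with a delta that is not defined. The protocol's Statistical Methods section describes its only efficacy model as follows: "A repeated measure mixed model will be used to assess within-subject changes from baseline".

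No sentence in either document calls the paired results descriptive or bars an efficacy conclusion from them.

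**The concern.** All the efficacy objectives are comparisons with placebo. A paired test against baseline answers a different question: whether scores moved, for whatever reason. Inclusion criterion 4 admits symptoms present "either continually or intermittently, with relapses not experienced pre-illness", so some movement over 26 weeks without any drug effect is plausible. Natural recovery, placebo response and fluctuation all enter a paired test in full, and a between-arm contrast removes them on average.

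At stake is the reporting of supportive results. Under SAP 5.2.2 a paired p-value can be read as statistical significance and a mean change beyond the MCID as clinical significance, both without reference to the control group. If the tests are run by arm, a significant active arm beside a non-significant placebo arm invites a conclusion that the randomised comparison may not support. The Bonferroni-Holm rule in SAP 3.1 does not name these tests.

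**Working it through.** **Inputs from the documents.** Total 80 subjects (SAP 6); 1:1 allocation (SAP 2.2), hence 80/2 = 40 per arm at most, because the efficacy set requires all four infusions; testing level from SAP 5.1.1: "all hypotheses will be tested at a 2-sided significance level of 0.05 and 95% confidence interval". The documents state no SD, effect size, power or expected natural course, so there is no design figure to reproduce.

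**Assumptions.** Zero treatment effect; the same mean improvement m in both arms; SD of change 2.5 cm, varied from 2.0 to 3.0; normally distributed changes.

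**Step 1: one arm's paired test.** With n = 40 the critical value is t(0.975, 39) = 2.023 and the noncentrality is m / (SD/√n). The probability p of a significant improvement is the upper tail of the noncentral t beyond 2.023. At SD 2.5, SD/√40 = 0.395.

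**Step 2: pattern by arm.** The arms are independent, so P(active significant, placebo not) = p(1 − p), which cannot exceed 0.25.

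| Shared improvement m | Noncentrality | p | p(1 − p) |
|---|---|---|---|
| 0.5 cm | 1.27 | 0.23 | 0.18 |
| 0.8 cm | 2.02 | 0.51 | 0.25 |
| 1.0 cm | 2.53 | 0.69 | 0.21 |
| 1.5 cm | 3.79 | 0.96 | 0.04 |
| 2.0 cm | 5.06 | >0.99 | 0.001 |

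For SD 2.0 to 3.0 and m 0.5 to 1.0 cm, the active-only pattern has probability 0.11 to 0.25. With 32 per arm the range is 0.13 to 0.25. With m = 0, p is 0.025 in the favourable direction.

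**Step 3: pooled reading.** The SAP does not say whether the paired test is run by arm or on all subjects. If pooled (n = 80, critical value 1.990), noncentrality at m = 0.5, 0.8 and 1.0 cm is 1.79, 2.86 and 3.58, and p is 0.42, 0.81 and 0.94. The active-only pattern cannot then arise, but a significant result is more likely and still has no placebo contrast.

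**Step 4: does the entry threshold alone produce the effect?** Inclusion criterion 4 applies the 5 cm threshold at screening, whereas SAP 5.1.2 measures change from Week 0. A simulation (4,000 trials per scenario, 40 per arm, normal scores with population mean 5 and SD 2, selected at screening ≥5, no treatment effect) separates the two. The ANCOVA contained treatment and baseline only.

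| Correlation screening–Week 0 | Correlation of each with Week 26 | Shared drift | Mean change from Week 0 | Active arm's paired test significant | ANCOVA type I error |
|---|---|---|---|---|---|
| 0.6 | 0.6 | 0 | 0.00 cm | 2.6% | 4.8% |
| 0.8 | 0.5 | 0 | −0.48 cm | 32% | 4.9% |
| 0.8 | 0.4 | 0 | −0.64 cm | 46% | 5.1% |
| 0.9 | 0.5 | 0 | −0.64 cm | 55% | 4.9% |
| 0.6 | 0.6 | 0.5 cm | −0.50 cm | 41% | 4.8% |
| 0.6 | 0.6 | 1.0 cm | −1.00 cm | 93% | 5.0% |

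In the first row the whole regression, about 0.63 cm, falls between screening and Week 0 and leaves the paired test at its nominal rate. How much remains after Week 0 depends on correlations that the documents do not give. Shared drift from any cause is enough to inflate the paired test. The between-arm ANCOVA is unaffected in every scenario.

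**The case against.** The strongest reply is that the plan already decides efficacy between arms. The primary hypothesis, the ANCOVA and the repeated measures model all compare HB-adMSCs with placebo, for primary and secondary endpoints alike. The paired tests rank only as secondary (SAP 5.1.1) or additional (SAP 5.2.2 and 5.3.1). This stands. A reader might infer that efficacy will be declared from within-arm change; the documents do not say so.

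The selection argument also needs restraint. A reader might infer that patients are enrolled at high severity and must regress. In fact one symptom of five at 5 cm on a 10 cm scale suffices, randomisation keeps a stratum with average score below 5 cm, symptoms may be continual as well as intermittent, and baseline is Week 0. The first row of the simulation shows that regression can be over by then. The fatigue scale, SF-36, PHQ-9 and non-neurological VAS have no entry threshold. So the point has to rest on shared improvement from any cause.

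The secondary hypothesis can be read as between-group, and the later sections of the SAP support that reading for the modelled analyses. The protocol's sentence on the mixed model is a one-line summary, and the next one promises correction for post-hoc comparisons. Both are matters of clarity.

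Finally, the 25% figure is the mathematical maximum of p(1 − p), and neither document makes active-only significance a decision rule. It should not be read as a type I error rate set against 2.5% or 5%.

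The reply leaves one thing unanswered: significance tests and an MCID rule without a placebo contrast are planned, and nothing limits what may be concluded from them.

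**Conclusion.** The point holds as a fault in supportive analyses and wording. It does not show that the primary efficacy conclusion rests on within-arm change.

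With an inert product and a shared improvement of 0.5 to 1.0 cm (SD 2.5 cm, 40 per arm), each arm's paired test is significant with probability 0.23 to 0.69. Run by arm, active-only significance occurs in about 18 to 25% of trials, falling to about 4% at 1.5 cm, where both arms are usually significant. These sizes rest on an assumed SD and natural course; with no shared improvement the paired test behaves nominally. What does not depend on those inputs is that a paired test, or a mean change set against an MCID, cannot separate treatment effect from improvement common to both arms. The change is worth making because it is cheap and the between-arm models it relies on are already planned.

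**What to change.** 1. SAP 3: define the secondary delta as HB-adMSCs minus placebo in change from baseline at Week 26.
2. Protocol, Statistical Methods: reword the mixed-model sentence so that it estimates the treatment-by-visit contrast already specified in SAP 5.2.2.
3. SAP 5.1.1, 5.2.2 and 5.3.1: replace the paired t-test and signed-rank p-values with within-arm means and 95% CIs, labelled descriptive.
4. SAP 5.2.2: stop using within-arm mean change against the MCID as evidence of efficacy; set any MCID comparison beside the between-arm difference and its CI.
5. Add one sentence stating that no efficacy conclusion rests on within-arm change.

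The cost is wording in the SAP and one protocol sentence, which will need the amendment route that the protocol describes. No between-arm inference is lost; the only loss is the set of within-arm p-values.
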